1.3. Sample Size and Power

A sample size of approximately 50 subjects is based on practical considerations and is considered to be sufficient to evaluate the primary objective of this study. The primary endpoint is the incidence of treatment-emergent Grade 3 or higher AEs up to Week 48. The Grade 3 or higher AE rate in Study GS-US-292-0112 in subjects that had mild to moderate renal impairment was 8.8% at Week 48 for the E/C/F/TAF arm. Therefore, with 50 subjects, and an assumed rate of Grade 3 or higher AEs being 10%, this study would provide 95% confidence for the primary endpoint to be within (1.7%, 18.3%) assuming normal approximation to binomial proportions.

CCI

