The percentages of subjects in the FAS with HIV-1 RNA < 50 copies/mL at Weeks 24 and 48, as determined using the US FDA-defined snapshot algorithm, were 87.3% (95% CI: 75.5% to 94.7%) and 81.8% (95% CI: 69.1% to 90.9%), respectively. The percentages of subjects with HIV-1 RNA \geq 50 copies/mL at Week 24 and Week 48 were 1.8% and 3.6%, respectively. The remaining subjects (10.9% at Week 24 and 14.5% at Week 48) had no virologic data in the corresponding window. All 6 subjects lacking virologic data in the Week 24 window and 7 of the 8 subjects lacking virologic data in the Week 48 window had prematurely discontinued study drug, with their last HIV-1 RNA value < 50 copies/mL.

The percentage of subjects in the FAS with HIV-1 RNA < 20 copies/mL at Week 48, as determined using the US FDA-defined snapshot algorithm, was 81.8% (95% CI: 69.1% to 90.9%). The percentage of subjects with HIV-1 RNA \geq 20 copies/mL at Week 48 was 3.6%. There was no virologic data in the Week 48 window for the remaining 8 (14.5%) subjects, 7 of whom had prematurely discontinued study drug with their last available HIV-1 RNA < 20 copies/mL.

At Week 48 there were no clinically significant differences between subgroups (age, sex, race, region, and study drug adherence rate) in the percentages of subjects with HIV-1 RNA < 50 copies/mL, determined using the US FDA-defined snapshot algorithm. Percentages of subjects with HIV-1 RNA < 50 copies/mL in each subgroup were generally similar to that observed in the overall study population.

When assessed using M = F and M = E imputation methods for missing data, the percentages of subjects with HIV-1 RNA < 50 copies/mL at Week 48 were 83.6% (95% CI: 71.2% to 92.2%) and 97.9% (95% CI: 88.7% to 99.9%), respectively. The percentage of subjects with HIV-1 RNA < 20 copies/mL at Week 48 was 83.6% (M = F) and 97.9% (M = E).

CD4 cell counts and CD4% remained stable through Week 48. The mean (SD) baseline CD4 cell count was 545 (239.2) cells/ μ L; the mean (SD) change from baseline at Week 48 was -16 (192.1) cells/ μ L. The mean (SD) baseline CD4% was 31.5% (9.41%); the mean (SD) change from baseline at Week 48 was 1.7% (4.10%).

Safety Results

In relation to the primary study endpoint, the incidence of treatment-emergent Grade 3 or higher AEs up to Week 48, Grade 3 or 4 AEs were reported for 32.7% of subjects (18 of 55).

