Exposures of TAF, EVG, and COBI were consistent with the range of historical data obtained following the administration of GEN (and Stribild® [EVG/COBI/FTC/TDF] in the case of EVG and COBI) to HIV-1 infected subjects with normal renal function. As expected, given the predominantly renal elimination of FTC and TFV, exposures of these analytes were higher in subjects on hemodialysis compared with historical data obtained following the administration of GEN to HIV-1 infected subjects with normal renal function or with mild to moderate renal impairment.

Conclusions

The conclusions from this Week 48 interim analysis are as follows:

- 1) Genvoya was well tolerated by virologically suppressed, HIV-1 infected adult subjects with ESRD on chronic hemodialysis. Common AEs were generally consistent with those expected in the study population.
- 2) Virologic suppression (HIV-1 RNA < 50 copies/mL) was maintained, and CD4 cell counts remained stable, through 48 weeks in virologically suppressed, HIV-1 infected adult subjects with ESRD on chronic hemodialysis who switched to GEN.
- 3) Exposures of TFV and FTC in virologically suppressed, HIV-1 infected subjects with ESRD on chronic hemodialysis receiving GEN were higher compared with historical data obtained following the administration of GEN to HIV-1 infected subjects with normal renal function or mild to moderate renal impairment. Exposures of TAF, EVG, and COBI were consistent with historical data from subjects with normal renal function.

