8.7. Sample Size

A sample size of approximately 50 subjects is based on practical considerations and is considered to be sufficient to evaluate the primary objective of this study. The Grade 3 or higher AE rate in Study GS-US-292-0112 in subjects that had mild to moderate renal impairment was 8.8% at Week 48 analysis for the E/C/F/TAF arm. Therefore, with 50 subjects, and an assumed rate of Grade 3 or higher AEs being 10%, this study would provide 95% confidence for the primary endpoint to be (1.7%, 18.3%) assuming normal approximation to binomial proportions.

CCI

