1.1. Study Objectives

The primary objective of this study is as follows:

- To evaluate the safety and tolerability of elvitegravir/cobicistat/emtricitabine/tenofovir alafenamide (EVG/COBI/FTC/TAF; E/C/F/TAF) fixed-dose combination (FDC) in HIV-1 infected adults with end stage renal disease (ESRD) on chronic hemodialysis (HD) at Week 48

The secondary objectives of this study are as follows:

- To evaluate the safety and tolerability of the E/C/F/TAF FDC in HIV-1 infected adults with ESRD on chronic HD at Week 96
- To evaluate the proportion of subjects receiving E/C/F/TAF FDC achieving virologic response (HIV-1 RNA < 50 copies/mL, as defined by the FDA snapshot analysis) at Weeks 24, 48, and 96
- To evaluate plasma pharmacokinetics (PK) of EVG, COBI, FTC, TAF, and tenofovir (TFV) in HIV-1 infected patients with ESRD on chronic HD
- To evaluate the safety and tolerability of bictegravir/emtricitabine/tenofovir alafenamide (B/F/TAF) FDC in HIV-1 infected adults with ESRD on chronic HD in the open-label extension phase

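### The precision stated for the primary endpoint (1.7% to 18.3%) rests on an adverse event rate from a healthier renal population and does not hold at the 32.7% this trial reports in hemodialysis patients

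*SAP*

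**What the plan says.** The primary objective in SAP 1.1 is safety and tolerability "in HIV-1 infected adults with end stage renal disease (ESRD) on chronic hemodialysis (HD) at Week 48". SAP 1.3 defines the endpoint: "The primary endpoint is the incidence of treatment-emergent Grade 3 or higher AEs up to Week 48".

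On sample size, SAP 1.3 first says (last word omitted): "A sample size of approximately 50 subjects is based on practical considerations and is considered to be sufficient to evaluate the primary objective of this". It then cites the rate in the earlier trial: "The Grade 3 or higher AE rate in Study GS-US-292-0112 in subjects that had mild to moderate renal impairment was 8.8% at Week 48". Next comes the planning value, "with 50 subjects, and an assumed rate of Grade 3 or higher AEs being 10" per cent. Protocol 8.7 carries the same text and, read as far as the upper limit, says: "an assumed rate of Grade 3 or higher AEs being 10%, this study would provide 95% confidence for the primary endpoint to be (1.7%, 18.3" per cent. SAP 1.3 adds that the endpoint would lie within that range. Both attribute the interval to the normal approximation.

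Protocol 1.4 describes GS-US-292-0112 as covering eGFR 30 to 69 mL/min. Protocol 4.2 and SAP 1.2 require eGFR below 15 mL/min and at least six months on hemodialysis.

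Protocol 1.2.5 gives this trial's interim Week 48 data and, with explicit reference to the primary endpoint, reports: "Grade 3 or 4 AEs were reported for 32.7% of subjects (18 of 55" treated). SAP 6.1 confirms that the primary analysis was already done for the Week 48 report. SAP 3.5 says that no formal testing is performed.

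**The concern.** The 10% planning rate is introduced as following from the 8.8%, but the visible text gives no reason why a rate seen in mild to moderate impairment should carry over to dialysis patients. Protocol 1.4 itself says that long-term safety at more advanced stages, including hemodialysis, had yet to be established. The mismatch could therefore be seen at design.

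The result now in hand confirms it. The protocol version that reports 32.7% in its introduction still states an interval ending at 18.3% in its sizing section. The SAP, finalized later, repeats that interval.

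With no hypothesis test, the stated interval is the only quantitative property of the sample size in the visible text. A reader who takes it at face value would expect an estimate good to about 8 points, centred near 10%. In its own population the trial has neither that precision nor that location.

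**Working it through.** **Inputs.** Assumed rate 10%, n = 50, two-sided 95%, normal approximation (SAP 1.3, Protocol 8.7). Observed endpoint 18 of 55 (Protocol 1.2.5). Treated subjects: 55 (Protocol 1.2.5; also the disposition mock table in SAP Appendix 6).

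**Formula.** Half-width = 1.96 × √(p(1 − p)/n).

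**The plan's figure.** 1.96 × √(0.10 × 0.90/50) = 1.96 × 0.0424 = 0.083. The interval is 10% ± 8.3 points, or 1.7% to 18.3%. This reproduces, so the arithmetic is right and the question is the input rate.

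**Same formula at the trial's own rate.**
- n = 50: 1.96 × √(0.327 × 0.673/50) = 1.96 × 0.0663 = 0.130.
- n = 55: 1.96 × √(0.3273 × 0.6727/55) = 1.96 × 0.0633 = 0.124.

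| Rate | n | Half-width (points) | Normal 95% interval |
|---|---|---|---|
| 10% (plan) | 50 | 8.3 | 1.7% to 18.3% |
| 20% | 50 | 11.1 | 8.9% to 31.1% |
| 30% | 50 | 12.7 | 17.3% to 42.7% |
| 32.7% | 50 | 13.0 | 19.7% to 45.7% |
| 40% | 50 | 13.6 | 26.4% to 53.6% |
| 18/55 = 32.7% | 55 | 12.4 | 20.3% to 45.1% |

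The change of rate alone widens the interval by a factor of 13.0/8.3 = 1.56. The five extra subjects recover a little: 12.4/8.3 = 1.49.

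**Does the choice of interval matter?** No. The exact (Clopper-Pearson) interval for 18/55 is 20.7% to 46.7%, with half-width (46.7 − 20.7)/2 = 13.0 points. The Wilson interval is 21.8% to 45.9%. Each lies wholly above 18.3%.

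**Is 32.7% compatible with the planning rate?** If the true rate were 10%, the binomial probability of 18 or more events in 55 would be about 3.7 in a million. At 18.3%, the top of the stated interval, it would be about 0.7%. These figures only test whether the planning rate fits this population. No decision in the trial depends on them.

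**The case against.** The strongest reply is that little turns on this. The sufficiency statement sits in the sentence about practical considerations, and the 8.8% comes after it as an illustration of precision. The 32.7% is the trial's own outcome and was not known when it was first sized. Enrollment is complete, the primary analysis will not be repeated, and once data exist the interval computed from them replaces any planned one. All of this stands, and it limits the point to what the documents state about precision. It does not rescue the statement: the population difference was known at design, and both documents repeat the interval after the Week 48 result was available.

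Four stronger readings are tempting, and the documents do not support them.

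- A reader might infer that 50 subjects was derived from the 8.8% and is therefore wrong. Both documents attribute the number to practical considerations.
- A reader might infer that the Week 96 adverse event endpoint carries the same error. SAP 8.1 and 8.2 use neither 8.8% nor 10% and plan counts and percentages without a confidence interval.
- A reader might infer that the interim conclusion in Protocol 1.2.5 lacks support. It says: "Common AEs were generally consistent with those expected in the study population". That concerns common events, not the incidence of Grade 3 or higher events.
- A reader might set 32.7% against 8.8% and infer excess harm from the study drug. Neither document makes that comparison, and different renal populations in a single-arm trial could not support it.

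Redacted text also follows both sizing paragraphs. That 8.8% is the only reference rate can be confirmed for the visible text only.

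**Conclusion.** The point holds as a fault in the stated precision. The interval of 1.7% to 18.3% is computed correctly from a rate that does not apply to hemodialysis patients. At the reported rate the half-width is 12.4 points (normal, n = 55) to 13.0 points (exact, n = 55; normal, n = 50), against 8.3 stated, so the interval is about one and a half times as wide. It also lies entirely above the stated one.

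This rests on the 18 of 55 in Protocol 1.2.5 being the primary endpoint, as that section says, and on the sizing text that is not redacted. No sample size, error rate, estimate or planned output changes. The correction is worth making because the current documents give two incompatible pictures of the primary endpoint, and because 8.8% stands in the sizing text without a statement that it is not a benchmark.

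**What to change.** In SAP 1.3, and in Protocol 8.7 if the protocol is amended again:

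1. Mark 1.7% to 18.3% as the superseded design assumption, based on a rate from subjects with less severe renal impairment.
2. State the precision in this population: at 18/55 (32.7%) the 95% half-width is about 12 to 13 points with 55 treated subjects. If a planning range is wanted, rates of 20% to 40% with 50 subjects give 11 to 14 points.
3. Say that the GS-US-292-0112 rate is not a comparator for patients on hemodialysis.

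This costs a few sentences and needs no new subjects, data or analyses. The one downside is that the stated precision becomes less favourable.

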2. TYPE OF PLANNED ANALYSIS

2.1. Data Monitoring Committee Analyses

The Week 12 Independent Data Monitoring Committee (IDMC) analysis was conducted after the first 25 subjects enrolled completed their Week 12 visit of the study or prematurely discontinued the study drug. The IDMC's role and responsibilities and the scope of analysis provided to the IDMC were provided in a mutually agreed upon charter, which defines the IDMC membership, meeting logistics, and meeting frequency.

2.2. Week 24 Analysis

A Week 24 analysis was conducted after all subjects enrolled either completed their Week 24 visit of the study or prematurely discontinued study drug.

2.3. Week 48 Analysis

A Week 48 analysis was conducted after all subjects enrolled either completed their Week 48 visit of the study or prematurely discontinued study drug.

2.4. Week 96 Analysis

A Week 96 analysis was conducted after all subjects enrolled either completed their Week 96 visit of the study or prematurely discontinued from the study.

2.5. Final Analysis

The final statistical analysis will be conducted after all subjects either complete the study or prematurely discontinue from the study.

This SAP describes the analysis plan for the final analysis.

3. GENERAL CONSIDERATIONS FOR DATA ANALYSES

The final analysis will include all data collected from the E/C/F/TAF and the B/F/TAF OL extension phases of the study. Separate tables and figures will be created for each phase unless otherwise specified. Data collected from both phases will be included in data listings. Data included in each phase are defined as follows:

E/C/F/TAF Phase Data

- For subjects who are never treated in the B/F/TAF OL extension phase of the study, all available data are considered as the E/C/F/TAF phase data.
- For subjects treated in the B/F/TAF OL extension phase of the study, E/C/F/TAF phase data are defined as data collected **up to** the B/F/TAF OL extension phase first dose date except for data on adverse events (AEs), concomitant medications, pregnancy, and death. For AEs, concomitant medications, pregnancy, and death, only data collected **prior to** the B/F/TAF OL extension phase first dose date are included.

B/F/TAF OL Extension Phase Data

- B/F/TAF OL extension phase data are only available from subjects who enter the B/F/TAF OL extension phase of the study. B/F/TAF OL extension phase data are defined as data collected **after** the B/F/TAF OL extension phase first dose date except for data on AEs, concomitant medications, pregnancy, and death. For AEs, concomitant medications, pregnancy, and death, data collected **on or after** the extension phase first dose date are included.

Analysis results will be presented using descriptive statistics. For categorical variables, the number and percentage of subjects in each category will be presented; for continuous variables, the number of subjects (n), mean, standard deviation (SD) or standard error (SE), median, first quartile (Q1), third quartile (Q3), minimum, and maximum will be presented.

By-subject listings will be presented for all subjects in the All Enrolled Subjects Analysis Set unless otherwise specified, and sorted by subject ID number, visit date, and time (if applicable). Data collected on log forms, such as AEs, will be presented in chronological order within a subject.

In general, age (in years) on the date of the first dose of E/C/F/TAF study drug will be used for analyses and presentation in listings. For screen failures, age on the date the informed consent was signed will be used. If only birth year is collected on the eCRF, “01 January” will be used for the unknown birth day and month for the purpose of age calculation; similarly, if only birth year and month are collected on the eCRF, “01” will be used for the unknown birth day for the purpose of age calculation.

In general, permanent discontinuation of study drug refers to premature discontinuation of study drug or completion of study drug.

3.1. Analysis Sets

Analysis sets define the subjects to be included in an analysis. Analysis sets and their definitions are provided in this section. Subjects included in each analysis set will be determined before data finalization and will be identified in a subtitle of each table, figure, and listing. A summary of the number and percentage of subjects in each analysis set will be provided.

3.1.1. All Enrolled Subjects Analysis Set

The **All Enrolled Subjects Analysis Set** will include all subjects who are enrolled into the study. This is the primary analysis set for by-subject listings.

3.1.2. B/F/TAF Enrolled Subjects Analysis Set

The **B/F/TAF Enrolled Subjects Analysis Set** will include all subjects who enrolled into the B/F/TAF OL extension phase of the study. This is the analysis set for by-subject listings that pertain to the B/F/TAF OL extension phase only.

3.1.3. E/C/F/TAF Full Analysis Set

The **E/C/F/TAF Full Analysis Set (FAS)** will include all subjects who (1) were enrolled in the study and (2) received at least 1 dose of E/C/F/TAF study drug. This is the primary analysis set for the E/C/F/TAF efficacy analyses.

3.1.4. B/F/TAF Full Analysis Set

The **B/F/TAF Full Analysis Set (FAS)** will include all subjects who (1) were enrolled in the study and (2) received at least 1 dose of B/F/TAF study drug. This is the primary analysis set for the B/F/TAF efficacy analyses.

3.1.5. E/C/F/TAF Safety Analysis Set

The **E/C/F/TAF Safety Analysis Set** will include all subjects who received at least 1 dose of E/C/F/TAF study drug. This is the primary analysis set for the E/C/F/TAF safety analyses.

3.1.6. B/F/TAF Safety Analysis Set

The **B/F/TAF Safety Analysis Set** will include all subjects who received at least 1 dose of B/F/TAF study drug. This is the primary analysis set for the B/F/TAF safety analyses.

3.1.7. B/F/TAF Plasma PK Analysis Set

The **B/F/TAF Plasma PK Analysis Set** will include all subjects who (1) were enrolled into the study, (2) received at least 1 dose of B/F/TAF study drug, and (3) have at least 1 nonmissing plasma PK concentration value for any analyte of interest reported by the PK lab. The B/F/TAF Plasma PK Analysis Set will be used for general B/F/TAF plasma PK analyses.

3.2. Subject Grouping

For all analyses, subjects will be grouped by treatment received. All subjects received E/C/F/TAF. Subjects who enrolled into the B/F/TAF OL extension phase also received B/F/TAF.

Subjects will be grouped under “GEN” for the E/C/F/TAF phase and under “GEN to OL B/F/TAF” for the B/F/TAF OL extension phase. In the subject listings, subjects who received only E/C/F/TAF will have treatment group of “GEN” and subjects who received E/C/F/TAF and OL B/F/TAF will have treatment group of “GEN to OL B/F/TAF”.

3.3. Strata and Covariates

This study did not use a stratified randomization schedule when enrolling subjects. No covariates will be included in efficacy or safety analyses.

3.4. Examination of Subject Subgroups

No subgroup analyses are planned.

3.5. Multiple Comparisons

Adjustments for multiplicity will not be made, because no formal statistical testing will be performed in this study.

3.6. Missing Data and Outliers

3.6.1. Missing Data

A missing datum for a given study analysis window may be due to any of the following reasons:

- A visit occurring in the window but data were not collected or were unusable
- A visit not occurring in the window
- A subject permanently discontinuing from the study before reaching the window

In general, values for missing data will not be imputed, unless methods for handling missing data are specified.

For missing last dose date of study drug, imputation rules are described in Section 3.8.1. The handling of missing or incomplete dates for AE onset is described in Section 8.3.5.2, and for concomitant medication in Section 8.6.2.

3.6.2. Outliers

Outliers will be identified during the data management and data analysis process, but no sensitivity analyses will be done to evaluate the impact of outliers on efficacy or safety outcomes, unless specified otherwise. All data will be included in the analyses.

3.7. Data Handling Conventions and Transformations

Laboratory data that are continuous in nature but less than the lower limit of quantitation (LLOQ) or above the upper limit of quantitation will be imputed as follows:

- A value that is 1 unit less than the limit of quantitation will be used for calculation of descriptive statistics if the datum is reported in the form of “ $< x$ ” (where x is considered the limit of quantitation). For example, if the values are reported as < 50 and < 5.0 , values of 49 and 4.9, respectively, will be used for calculation of summary statistics. An exception to this rule is any value reported as < 1 or < 0.1 , etc. For values reported as < 1 or < 0.1 , a value of 0.9 or 0.09, respectively, will be used for calculation of summary statistics.
- A value that is 1 unit above the limit of quantitation will be used for calculation of descriptive statistics if the datum is reported in the form of “ $> x$ ” (where x is considered the limit of quantitation). Values with decimal points will follow the same logic as above.
- The limit of quantitation will be used for calculation of descriptive statistics if the datum is reported in the form of “ $\leq x$ ” or “ $\geq x$ ” (where x is considered the limit of quantitation).

Logarithm (base 10) transformation will be applied to HIV-1 RNA data for efficacy analyses. HIV-1 RNA results of “No HIV-1 RNA detected” and “ < 20 copies/mL HIV-1 RNA detected” will be imputed as 19 copies/mL for analysis purposes.

3.8. Analysis Windows

3.8.1. Definition of Study Day

Study Day 1 is defined as the day when the first dose of E/C/F/TAF study drug was taken, as recorded on the Study Drug Administration eCRF form.

B/F/TAF Study Day 1 is defined as the day when the first dose of B/F/TAF study drug was taken, as recorded on the Study Drug Administration eCRF form.

Study Days are calculated relative to Study Day 1 and B/F/TAF Study Day 1. For events that occurred on or after Study Day 1, study days are calculated as (visit date minus Study Day 1 plus 1). For events that occurred prior to Study Day 1, study days are calculated as (visit date minus Study Day 1).

E/C/F/TAF Last Dose Date is the latest of E/C/F/TAF study drug end dates recorded on the Study Drug Administration eCRF form with “Permanently Withdrawn” box checked for subjects who prematurely discontinued study drug or who completed study drug according to the Study Drug Completion eCRF.

If the date of E/C/F/TAF last dose is missing (eg, only year of last dose is known or completely missing due to lost to follow-up) for subjects who prematurely discontinued or completed study drug, the latest of the E/C/F/TAF study drug start dates and end dates, the clinic visit dates, and the laboratory visit dates, excluding the date of the 30-day follow-up visit and any dates on or after the first dose of B/F/TAF if applicable, will be used to impute the last dose date. For other partial missing last dose dates, please see programming specifications ([Appendix 7](#)) for imputation rule details.

B/F/TAF Last Dose Date is the latest of B/F/TAF study drug end dates recorded on the Study Drug Administration eCRF form with “Permanently Withdrawn” box checked for subjects who prematurely discontinued study drug or who completed study drug according to the Study Drug Completion eCRF.

If the date of B/F/TAF last dose is missing (eg, only year of last dose is known or completely missing due to lost to follow-up) for subjects who prematurely discontinued or completed study drug, the latest of the B/F/TAF study drug start dates and end dates, the clinic visit dates, and the laboratory visit dates, excluding the date of the 30-day follow-up visit and any dates before the first dose of B/F/TAF, will be used to impute the last dose date. For other partial missing last dose dates, please see programming specifications ([Appendix 7](#)) for imputation rule details.

Last Study Date is the latest of E/C/F/TAF or B/F/TAF study drug start date and end date, clinic visit dates, and laboratory visit dates, including the 30-day follow-up visit date, for subjects who prematurely discontinued the study or who completed the study according to Study Completion eCRF.

Baseline value for the E/C/F/TAF phase is defined as the last value obtained on or prior to Study Day 1 for all assessments. Baseline value for the B/F/TAF OL extension phase is defined as the last value obtained on or prior to B/F/TAF Study Day 1 for all assessments.

